### 3.2. Hypothesis (if applicable)

- 1) Participants will report the 6-week tobacco treatment intervention is acceptable and they are satisfied with the intervention.
- 2) Participants who complete the preference driven culturally-tailored tobacco treatment intervention will have higher rates of tobacco abstinence compared to participants in the control arm.

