##### **4.2.2. Eligibility Criteria**

###### Inclusion Criteria:

- Self-identify as an African American woman
- Aged 18 years to 69 years
- Currently smoke 5 cigarettes per day or more
- Has smoked daily for the past one year
- Able to provide informed consent
- Generally good health as determined by medical history

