**5.3. Study intervention (including schedule of events and study visits)**

The study intervention includes a combination of tobacco treatment counseling sessions using motivational interviewing by certified tobacco treatment specialists, randomization to either (a) culturally-tailored tobacco treatment intervention or (b) preference driven culturally-tailored tobacco treatment intervention, home CO monitoring, and combination

Study Number: Pro2022-0894	05.02.2023
----------------------------	------------

nicotine replacement therapy over-the-counter medication and the Nicotine Replacement Therapy (NRT) patch kit + NRT lozenge kit.

After a participant is consented and enrolled into the study, they will complete a baseline survey and be scheduled for weekly telephone calls with a certified tobacco treatment specialist. After the baseline survey is completed, a personal home CO monitor will be ordered for the patient and shipped directly to their home. Instructions on how to use will be emailed to the participant and reviewed in the 1st weekly counseling session with the CTTS.

The tobacco intervention content will be delivered by telephone by a CTTS weekly. The weekly activities including plan to reduce total cigarette intake, and dosing chart for the nicotine replacement (based upon the National Comprehensive Cancer Network's Evidence-Based Tobacco Treatment Guidelines (2022) is listed below by week:

Week	Tobacco Intervention Content	Nicotine Replacement Therapy
Orientation (Baseline)	
 
Overview of Study
 
Informed Consent
 
Baseline Surveys
 
	
Dosing Chart
 
>10cigarettes/day: Initially one 21mg patch daily for 6 weeks; then one 14mg patch daily for 2 weeks, then one 7mg patch daily for 2 weeks, then stop.
 
≤10cigarettes/day: initially one 14mg patch daily for 6 weeks then one 7mg patch daily for 2 weeks, then stop.

Session 1	
 
Review Quit Plan
 
Baseline CO Level
 
	
Session 2	
 
Behavior Target: Decrease # of Cigarettes Daily by 20%
 
	
 
Start NRT: Nicotine Patch (see dosing chart) + 2mg NRT lozenges prn
 

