Session 3	
 
Behavior Target: Decrease # of Cigarettes Daily by additional 20% (total = 40%)
 
	
 
Continue NRT: Nicotine Patch (see dosing chart) + 2mg NRT lozenges prn
 

Session 4	
 
Behavior Target: Decrease # of Cigarettes Daily by additional 20% (total = 60%)
 
	
 
Continue NRT: Nicotine Patch (see dosing chart) + 2mg NRT lozenges prn
 

Session 5	
 
Behavior Target: Decrease # of Cigarettes Daily by additional 20% (total = 80%)
 
	
 
Continue NRT: Nicotine Patch (see dosing chart) + 2mg NRT lozenges prn
 

Session 6	
 
Behavior Target: Decrease # of Cigarettes Daily by additional 20% (total = 100% = QUIT)
 
	
 
Continue NRT: Nicotine Patch (see dosing chart) + 2mg NRT lozenges prn
 

Final Session	
 
Assess how participant is doing. How many cigarettes (if any) smoking per day. Answer any questions including questions about NRT tapering schedule
 
Assess NRT use, response, issues
 
	
 
Taper NRT per protocol
 

During the Week 1 telephone call with the CTTS, the participant will be educated about combination nicotine replacement therapy over-the-counter medication and the Nicotine Replacement Therapy (NRT) patch kit + NRT lozenge kit will be mailed to the participant's home.

The 6 tobacco treatment counseling sessions will use motivational interviewing by a CTTS to address quitting motivations, benefits of tobacco treatment, overcoming nicotine dependence and practical ways to handle triggers, nicotine withdrawal management, stress management, healthy eating and activity, and relapse prevention.

Study Number: Pro2022-0894	05.02.2023
----------------------------	------------

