#### 5.4. Assignment / randomization (if applicable) n/a

#### 5.5. Section of instruments.

The primary outcome of this feasibility and usability pilot study is satisfaction with the processes of the study. A Satisfaction and Usability Questionnaire will be used that assesses participant thoughts and opinions about the intervention components, duration, outreach, and methods.

In addition, we will assess sociodemographic data including gender, race, marital status, education, and employment status will be gathered along with data on health status, history of chronic disease, and height and weight. Nicotine addiction will be measured by the Fagerström Questionnaire. Stage of change for smoking will be assessed uses the processes of change, self-efficacy for behavior change, and decisional balance (pros and cons of change). *Biochemical Validation*. Expired carbon monoxide measures will be used to confirm smoking status. CO levels < 9 ppm will be used as the cutoff.

Timing of Assessments	Baseline	Weekly	6 weeks post study start
Sociodemographic & Health Status Questionnaire	X		
Fagerstrom Test for Nicotine Dependence	X	X	X
CO Monitor	X	X	X
Stage of Change for Tobacco Cessation	X		X
Usability			X
Acceptance & Satisfaction			X

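### Abstinence is to be compared between arms, but the only stated criterion is an untimed home CO reading below 9 ppm, so continuing light smokers could be counted as abstinent

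*Combined protocol and SAP*

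**What the plan says.** Section 3.2, Hypothesis 2, expects that women completing the preference-driven intervention "will have higher rates of tobacco abstinence compared to participants in the control arm". The study design row of the Summary likewise describes a comparison of cessation rates.

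Section 5.5 gives the one criterion for smoking status: "Expired carbon monoxide measures will be used to confirm smoking status. CO levels < 9 ppm will be used as the cutoff". The assessment table there lists sociodemographics and health status, the Fagerström test, CO, stage of change, usability, and acceptance and satisfaction. It has no row for self-reported abstinence or cigarettes per day. No look-back is named. Of the two other smoking-related rows, the Fagerström test is given a different purpose ("Nicotine addiction will be measured by the Fagerström Questionnaire"), and stage of change is described through processes of change, self-efficacy and decisional balance.

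The CO reading is taken at home: "a personal home CO monitor will be ordered for the patient and shipped directly to their home" (section 5.3). Neither a time of day nor a time since the last cigarette is set.

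Cigarettes per day is asked in counselling, at the week 3 call (section 4.3) and at an undated Final Session (section 5.3).

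On consumption, section 4.2.2 admits women who "Currently smoke 5 cigarettes per day or more", with no upper limit. The Session 5 target in section 5.3 is "Decrease # of Cigarettes Daily by additional 20% (total = 80" percent), and Session 6 is the quit target. The final assessment is 6 weeks after study start (sections 5.5 and 5.6).

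**The concern.** Expired CO reflects recent smoking and falls within hours. It separates a heavy smoker from a non-smoker well, and a woman on one or two cigarettes a day from a non-smoker poorly. The reduction plan aims to bring women down to low consumption just before the quit step, so a woman who follows it but does not quit may be in the range where a spot reading discriminates least.

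If CO alone settles her status, cutting down can be recorded as quitting. Nothing in the plan says how to class a woman who tells the counsellor she smokes 2 a day and blows 5 ppm. A descriptive abstinence rate still needs a defined numerator.

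**Working it through.** **1. The plan's own figure.** Section 5.3 lists cumulative targets of 20, 40, 60, 80 and 100%. Remaining use = baseline × (1 − 0.2k), for k = 1 to 5, reproduces them. At Session 5 (k = 4), 20% of baseline remains:

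- 5 a day → 1
- 10 a day → 2
- 20 a day → 4, if such women enrol
- 30 a day → 6
- 40 a day → 8

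Section 4.3 can be read as taking each 20% off current use. Four such steps leave 0.8⁴ = 41% of baseline (5 → 2.0, 10 → 4.1, 20 → 8.2), which does not match the stated 80%. All of these are targets, not observed use.

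**2. CO model (assumed; the documents give no kinetics).** Boost b = 3–8 ppm per cigarette, half-life h = 3–6 h, background 2 ppm, 16 waking hours, same pattern every day. Mid-range values: b = 5, h = 5. Just after a cigarette, CO = 2 + b × Σ 0.5^(t/h) / (1 − 0.5^(24/h)), where t runs over the hours since each of the day's cigarettes. Time above 9 ppm after a peak = h × log₂((peak − 2)/7).

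*One a day.*
- Highest setting (b = 8, h = 6): peak = 2 + 8/0.9375 = 10.53 ppm. Time above 9 = 6 × log₂(8.533/7) = 1.71 h. Share below 9 = 1 − 1.71/16 = 89%.
- Mid-range: peak = 2 + 5/0.9641 = 7.19 ppm, so 100% below.

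*Two a day, 8 h apart, the first on waking.*
- Highest setting: the peaks are 11.88 and 13.92 ppm, with 2.98 h and 4.61 h above 9. Share below = 1 − 7.59/16 = 52.6%.
- Mid-range: highest peak = 2 + 5 × (1 + 0.5^1.6)/0.9641 = 8.90 ppm, so 100% below.

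*Two a day, one hour apart, mid-range.*
- Peak = 2 + 5 × (1 + 0.5^0.2)/0.9641 = 11.70 ppm, above 9 for 5 × log₂(9.70/7) = 2.35 h.
- If the second is smoked half an hour before bed, only 0.5 h of this is waking time: 1 − 0.5/16 = 97% below.
- If the pair is smoked earlier in the day: 1 − 2.35/16 = 85% below.
- At the highest setting, the earlier pair gives 1 h + 7.23 h above 9, so 1 − 8.23/16 = 49% below.

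*Four a day, every 4 h from waking.*
- Highest setting: the lowest waking value, just before the second cigarette, is 2 + 12.86 × 0.5^(4/6) = 10.1 ppm, so 0% below.
- Lowest setting (b = 3, h = 3): the highest peak is 6.87 ppm, so 100% below.
- Mid-range: about 51%, or about 58% with cigarettes at interval midpoints.

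*Six and eight a day (midpoint spacing, mid-range).* About 17% and 6%.

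**3. A second set of assumptions** (2–6 ppm, 2–8 h, background 1–3 ppm; 45 settings), counting settings below 9 ppm:

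| Cigarettes a day | 1 h after the last | 8 h after the last |
|---|---|---|
| 1 | 44/45 | 45/45 |
| 2 | 36/45 | 45/45 |
| 4 | 24/45 | 42/45 |

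**4. Weight of one error.** With 10 women per arm (section 4.1), one misclassified woman moves an arm's rate by 1/10 = 10 percentage points.

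**5. Calendar.** If sessions are weekly, the Session 6 quit target falls at about week 6, which is also when the final assessment is due. A fully adherent woman could then have fewer than 7 smoke-free days.

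**The case against.** **Some self-report is implied.** Section 5.5 presents CO as biochemical validation, which presupposes a reported status to validate, and the Final Session asks about cigarettes smoked. A reader might infer that the plan makes CO alone decisive, or that smoking is never asked about. The documents support neither: no passage says that CO below 9 ppm overrides reported smoking. Appendix 1 (measures) is listed but its content is not in the text available, so an item inside an instrument cannot be ruled out. What stands is narrower: reported smoking is not a scheduled outcome, has no look-back, and is not combined with CO in any definition.

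**Consumption and kinetics are not document facts.** Saying that all non-quitters would smoke 1–4 a day needs a 20-a-day ceiling that the plan does not set, and treats targets as behaviour. The CO figures are assumed throughout. At 4 a day the range is uninformative, and heavier smokers would usually be detected in daytime. Nor can one say that every such woman reads below 9 ppm on waking: four cigarettes bunched in the evening can leave a waking value of 12.8 ppm within the same ranges. This objection stands, and limits the point to the lightest smokers.

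**Consequence is limited.** Abstinence is not among the declared primary outcomes (feasibility, acceptability, satisfaction) or the secondary outcome (stage of change). Section 5.8.2 makes all analysis descriptive. With 10 per arm, Hypothesis 2 could not be settled even with perfect classification, so the CO criterion cannot be blamed for that. CO is measured alike in both arms, and nothing shows a differential error.

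**Conclusion.** The concern holds in limited form. Abstinence is compared but not defined, and the only stated criterion is an untimed home CO reading that women smoking 1–2 cigarettes a day could often pass.

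Under the first set of assumptions, with even spacing, such women read below 9 ppm for about 52–100% of the waking day. At mid-range values the share is about 97–100% with even spacing or a late-evening pair. Bunching two cigarettes earlier in the day lowers it to about 85% at mid-range and about half at the highest setting. At 4 a day the result is 0–100%, so no claim is made there.

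The supportable conclusion is that continuing light smokers could be counted as abstinent, at 10 percentage points of an arm's rate each. That abstinence will be overstated, or that the arm difference is biased, does not follow. The effect is confined to the descriptive abstinence comparison in Hypothesis 2 and the Summary.

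**What to change.** - **Definition (section 5.5).** Class a woman as abstinent only if she reports no smoking over a look-back named in the protocol and her CO is below 9 ppm. Any reported smoking counts as smoking, whatever the CO value.
- **Data.** Add self-reported smoking and cigarettes per day to the weekly and 6-week columns and to the REDCap interview. Record hours since the last cigarette with each CO reading.
- **Reporting.** Report reduction separately from abstinence.
- **Look-back.** Choose one that fits between the Session 6 quit target and the final assessment, for example since the quit target or the past 24 hours. Alternatively, measure abstinence at the Final Session, if that falls at least the look-back length after Session 6. The 7-day window in section 3.1 belongs to the overarching study. Carried over unchanged, it could class adherent quitters as smokers. The timing in sections 5.3, 5.5 and 5.6 must be reconciled, including a date for the Final Session.

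The cost is two or three questions in calls that already take place, plus wording in section 5.5; treatment and sample size are unchanged. The reported abstinence rate may be lower, and a short look-back supports a weaker abstinence claim.

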#### 5.6. Data management (data collection, source and storage)

Data at baseline and end of study (6 weeks post study start for each participant) will be collected by phone. Self-report data will be gathered via a standardized interview using REDCap (Research Electronic Data Capture). REDCap is a secure web-based application for building and managing online surveys and databases. REDCap provides audit trails for tracking data manipulation and user activity as well as export procedures for secure data downloads to common statistical packages.

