### 3.4. Primary Outcome Variable(s)

Feasibility, acceptability and satisfaction with the content of the educational content and the tobacco treatment intervention.

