#### Intervention Content

#### **Culturally-tailored Tobacco Treatment Intervention (Arm 1) vs. Preference-Driven Culturally-tailored Tobacco Treatment Intervention (Arm 2)**

In addition to weekly cessation counseling by a CTTS for 6 weeks covering the Tobacco Intervention Content outlined above in Table 1, participants will receive weekly Content Newsletters emailed after their weekly cessation counseling session.

Participants randomized to Arm 1 will receive the Culturally-tailored Content Newsletters and participants randomized to Arm 2 will complete the one-item Control Preference Scale and receive either an Active Content Newsletter or Passive Content Newsletter. The Control Preference Scale question is:

*In terms of making decisions about your health care with your provider, which ONE of the following best describes how you would like to make these decisions?*

-  *Make the final selection about which treatment I will receive.*
-  *Make the final selection after seriously considering my provider's opinion.*
-  *Have my provider and I share responsibility for deciding what treatment is best.*
-  *Have my provider make the final decision but consider my opinion.*
-  *Leave all decisions regarding treatment to my provider.*

Individuals will be classified as follows:

1 or 2 = Active Control Preference

3 or 4 = Collaborative Control Preference

5 = Passive Control Preference

Participants will receive weekly cessation counseling by a CTTS for 6 weeks covering the Tobacco Intervention Content outlined above in Table 1. Participants will receive variations (active vs. passive control preference) of the weekly Content Newsletters emailed after their weekly cessation counseling session:

#	Active Content Newsletter	Passive Content Newsletter
1	Addresses Race and Smoking, History of Research Distrust, and Concerns about Nicotine Replacement Therapy (NRT)	Concerns about Nicotine Replacement Therapy (NRT)
2	Addresses Reasons and Motivations for Quitting, Nicotine as an Addiction, Coping Response Training, Tracking Your Triggers	Nicotine as an Addiction, Coping Response Training, Tracking Your Triggers
3	Addresses Benefits of Quitting, Stressors Unique to African Americans, Discrimination & Racism, Ways to Cope	Addresses Benefits of Quitting, Ways to Cope
4	Addresses Mood and Depression Among African Americans, Buddy System	Buddy System

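### The satisfaction part of the primary outcome is collected by phone interview, the same channel as the counselling it rates, with no self-completion option and no stated interviewer independence

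*Combined protocol and SAP*

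**What the plan says.** Section 5.5 names the outcome: "The primary outcome of this feasibility and usability pilot study is satisfaction with the processes of the study". Section 3.4 words it more broadly: "Feasibility, acceptability and satisfaction with the content of the educational content and the tobacco treatment intervention". The instrument is described in 5.5: "A Satisfaction and Usability Questionnaire will be used that assesses participant thoughts and opinions about the intervention components, duration, outreach, and methods". The assessment table there schedules usability, acceptance and satisfaction once, at 6 weeks.

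On collection, section 5.6 states: "Data at baseline and end of study (6 weeks post study start for each participant) will be collected by phone". It continues: "Self-report data will be gathered via a standardized interview using REDCap". It does not say who conducts the interview. The same section describes REDCap as a system that can run online surveys.

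The intervention being rated consists largely of weekly telephone sessions with a certified tobacco treatment specialist (sections 4.3 and 5.3). Email is already used with participants. Section 4.3 says that "participants will receive weekly Content Newsletters emailed after their weekly cessation counseling session", and section 5.3 has the instructions for the carbon monoxide monitor emailed as well.

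The first hypothesis in section 3.2 is: "Participants will report the 6-week tobacco treatment intervention is acceptable and they are satisfied with the intervention". No satisfaction threshold is set, and section 5.8.2 limits the analysis to description.

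**The concern.** A participant is asked to judge the calls, the outreach and the study methods, and she gives that judgement aloud over the same channel. Nothing in the plan separates the person asking from the person who counselled her, and she has no private way to answer. In that setting some women may give a kinder answer than they would on a form completed alone.

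Any such courtesy effect would raise the reported satisfaction level, which is what the first hypothesis predicts. The study could not recognise it afterwards. Only one mode is used, no external benchmark or threshold is set, and 20 descriptive responses cannot separate a well-liked programme from polite answers. What is at stake is the credibility of the absolute satisfaction figure that this pilot exists to supply to the larger study.

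**Working it through.** **1. Passages side by side**

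| Question | What the plan says | Where |
|---|---|---|
| What is measured? | Opinion of the intervention and study methods, once, at 6 weeks | 5.5 |
| How is it collected? | By phone, as a standardized interview entered in REDCap | 5.6 |
| Who asks? | Not stated | 5.6 |
| How is the rated intervention delivered? | Weekly by phone, by the specialist | 4.3, 5.3 |
| Is a private route available? | REDCap can run online surveys; email is in use | 5.6, 4.3, 5.3 |
| Which result is hypothesised? | Favourable ratings, no threshold | 3.2 |

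The plan gives no expected satisfaction rate, threshold or power figure, so there is no stated number to reproduce.

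**2. Weight of one answer**

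With 20 women, 10 per arm (section 4.1), one changed answer moves the overall proportion by 1/20 = 5 percentage points and the proportion in her arm by 1/10 = 10 points.

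**3. Illustration under assumed values**

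Let p be the true proportion satisfied and f the share of the remaining women who nevertheless report satisfaction to an interviewer. Neither is in the documents. The expected observed proportion is p + f(1 − p).

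| True p | f = 0.10 | f = 0.25 | f = 0.50 |
|---|---|---|---|
| 60% | 64% | 70% | 80% |
| 70% | 73% | 77.5% | 85% |
| 80% | 82% | 85% | 90% |

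In counts for the first row: if 12 of 20 are truly satisfied, 8 are not. Two courtesy answers (f = 2/8 = 0.25) give 14/20 = 70%. Four (f = 4/8 = 0.50) give 16/20 = 80%.

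**4. Could the data reveal such a shift?**

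Exact 95% intervals (Clopper-Pearson) are:
- 12/20: 36% to 81%
- 14/20: 46% to 88%
- 16/20: 56% to 94%

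These overlap heavily. Because every answer is collected the same way, there is also no internal comparison from which to estimate a mode effect.

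**5. Effect on a possible reading of the result**

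Suppose a reader took at least 16 of 20 satisfied as success. That mark is assumed and is not in the plan. With true p = 70%, the binomial chance of reaching it is 0.24 at f = 0, 0.34 at f = 0.10, 0.52 at f = 0.25 and 0.83 at f = 0.50.

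**The case against.** The strongest reply is that phone collection is a defensible choice for completeness. In a sample of 20 each missing questionnaire costs 5% of the data, and women who ignore an emailed link may be the less satisfied ones, which inflates the result by another path. On the assumed 12 of 20, if 4 of the 8 women who are not satisfied did not respond, the figure would read 12/16 = 75%. Email access is not an eligibility criterion (4.2.2), and 6.4 allows the consent copy to go by post. This part stands. It is why the phone must remain as back-up and why the mixed-mode downside has to be stated.

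A second reply is that safeguards exist: the interview is standardized, data are coded by study ID, and results are reported in aggregate (4.4.1, 5.6, 6.3). These protect the records and the consistency of the questions. They do not make the answer private at the moment it is spoken.

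A third reply is that the bias is only presumed. That is correct. The plan contains no data on the direction or size of a mode effect, and the response scale cannot be seen because the measures appendix is listed but not reproduced.

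Several stronger readings are tempting, and the documents do not support them:
- **The counsellor conducts the interview.** Section 5.6 names no interviewer. It only leaves the possibility open.
- **The questionnaire is given on the Final Session call.** The table in 5.3 puts no date on that session, so it need not coincide with the 6-week assessment.
- **The newsletter topic on research distrust implies inflated ratings.** It is intervention content in the active version only, and distrust could equally lower ratings.
- **The difference between arms is compressed.** Both arms use the same mode, and compression would need a ceiling on a scale that is not shown.

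**Conclusion.** The concern holds as a risk to one part of the primary outcome. Satisfaction and acceptability are spoken opinions, collected over the channel being rated, with no private alternative and no stated independence of the interviewer. If courtesy answers occur, they push the absolute satisfaction level towards the first hypothesis, and the trial's own data could neither detect nor remove the shift.

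The size is unknown. What is certain is the weight of each answer, 5 percentage points of 20. The move from 60% to 70–80% rests wholly on an assumed true rate and an assumed 2 to 4 courtesy answers. Across the assumed values tabulated above, the inflation runs from 2 points (true 80%, f = 0.10) to 20 points (true 60%, f = 0.50).

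Two limits apply. Sections 3.3 and 3.4 also list feasibility as primary, and any feasibility measure based on process counts would be unaffected. The comparison of arms is not the main issue. A reader might infer that the plan's satisfaction result will be biased; the documents support only that it is exposed to bias without a stated safeguard.

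**What to change.** Amend section 5.6 as follows:
- At 6 weeks, email the Satisfaction and Usability Questionnaire to every randomised woman as a self-completed REDCap link.
- Tell each woman that her counsellor will not see her individual answers.
- Use a phone interview only as back-up for women who do not respond, done by an existing team member who did not counsel that woman.
- Record the mode of each response and report satisfaction by mode as well as overall.

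The other 6-week measures can stay as planned. No new system is needed, since REDCap and participant email are already in the plan. The cost is a wording change, one survey link and some reminders. The remaining downside is two collection modes in a small sample, with mode possibly related to how engaged a woman was. Results by mode should therefore be read descriptively and not used for adjustment.
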